Eligible participants were randomized in a 1:1:1:1 ratio to receive either topical CsA 0.1% (CsA group), topical Tacrolimus 0.1% (Tacrolimus group), LLLT combined with topical CsA 0.1% (LLLT–CsA group), or LLLT combined with topical Tacrolimus 0.1% (LLLT–Tacrolimus group). A random allocation sequence was generated using Randomizer.app (PWA Labs Inc., CA, USA) by an ophthalmologist who was not otherwise involved in the study. The same individual was responsible for performing the LLLT procedure and providing CsA 0.1% or Tacrolimus 0.1% according to group allocation. Treatment allocation was concealed from the ophthalmologists and optometrists involved in the study until the conclusion of data analysis.

- Photobiomodulation: LLLT was administered using the eye-light[®] device (Espansione Group, Bologna, Italy), which employs Light ModulationTM technology. The treatment was delivered with a wavelength of 625 nm and a radiance of 35 mW/cm², resulting in a total energy dose of approximately 32 J/cm² applied to the facial and eyelid regions with eyes

closed. Three 15-minute sessions were performed at weekly intervals starting at the baseline visit. The same protocol was repeated at the 6-month follow-up, following evaluation of the outcome measures.

- Topical CsA and Tacrolimus preparation: CsA 0.1% and Tacrolimus 0.1% were prepared as sterile aqueous microemulsions. The formulation excluded ethanol and preservatives, using the the most functional and minimal number of excipients to minimize adverse events: ethoxylated hydrogenated castor oil, polysorbate 80, sodium chloride, sodium hyaluronate, phosphate buffer (pH: 6.8 - 7.2), and water for injections. A concentrated 10 mg/mL emulsion was first prepared in a biological safety cabinet, then mixed under sterile cleanroom conditions with a buffered base solution containing the other excipients. Final sterilization was performed using 0.22 μ m filtration under a Grade A hood, followed by packaging in sterile dropper bottles. CsA 0.1% and Tacrolimus 0.1% were clear and odorless, thereby minimizing sensory differences for the participants. Moreover, the bottles were identical in both appearance and labeling, which helped ensure that patients remained masked to their treatment allocation. Patients were instructed to apply the medications every 12 hours.

Assessment of the outcome measures

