Title: Efficacy of Low-Level Light Therapy in Combination with Topical Non-Steroidal Immunosuppressants for the Treatment of Dry Eye Disease: A Multicenter, Randomized, Single-Masked, Active-Controlled Trial.

NCT number: ID not yet assigned.

Date: 10/13/2025.

Statistical analysis

Statistical analyses were conducted with SPSS statistics software, version 25.0 (IBM Corp., Armonk, NY, USA). The sample size was estimated using the GRANMO calculator, version 8.0 (Registre Gironí del Cor, Barcelona, Spain). It was calculated based on assumed mean difference in OSDI scores between groups at 6 months after the intervention onset, with a mean value of -8.05 ± 2.78 points (Range: -0.75 to -12.74). This assumed difference were based on the findings of a pilot study with 20 eyes of 10 patients in each group. With these assumptions, a sample size of 24 eyes per group would yield a power $> 80\%$ and a statistically significant paired difference of 95% confidence. A 5% lost to follow-up was considered when calculating sample size.

The Kolmogorov-Smirnov test confirmed that the outcome measures met the normality criteria, allowing for the application of parametric tests. A repeated measures ANOVA with Bonferroni-adjusted post hoc tests was conducted to assess intra-group changes. For each group, the change (Δ) was calculated for the intervals between baseline and month 6 ($M6$), baseline and month 12 ($M12$), and month 6 to month 12 ($M6 \rightarrow M12$), using the following formulas:

$$\Delta_{M6} = M6 - \text{Baseline} \quad \Delta_{M12} = M12 - \text{Baseline} \quad \Delta_{M6 \rightarrow M12} = M12 - M6$$

A one-way ANOVA with Bonferroni-adjusted post hoc tests was also performed to compare inter-group differences. The difference between the changes (D_Δ) observed within each group over the mentioned intervals was computed for each pair of groups, using the following formulas:

$$D_{\Delta M6} = \Delta_{M6}^{(x)} - \Delta_{M6}^{(y)} \quad D_{\Delta M12} = \Delta_{M12}^{(x)} - \Delta_{M12}^{(y)} \quad D_{\Delta M6 \rightarrow M12} = \Delta_{M6 \rightarrow M12}^{(x)} - \Delta_{M6 \rightarrow M12}^{(y)}$$

For all $x \neq y \rightarrow x, y \in \{CsA, Tacrolimus, LLLT-CsA, and LLLT-Tacrolimus groups\}$

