Categorical variables were compared using the Chi-squared test (χ^2). Statistical significance and clinical relevance were evaluated. Statistical significance was defined as a P -value less than 0.05. Clinical relevance was estimated using partial eta squared (η_p^2) for ANOVAs, Cohen's d_z for within-group comparisons, and Cohen's d_s for between-group comparisons in Bonferroni-adjusted post hoc tests. According to Cohen's benchmarks, effect sizes were classified as small ($\eta_p^2 < 0.06$; $d_z = d_s < 0.5$), moderate ($\eta_p^2 \geq 0.06$ and < 0.14 ; $d_z = d_s \geq 0.50$ and < 0.8), and large ($\eta_p^2 \geq 0.14$; $d_z = d_s \geq 0.80$).

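### Single-step Bonferroni over the six between-group pairs is valid but inefficient: Holm over the same six has the same 5% family-wise bound and never rejects less

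*SAP*

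**What the plan says.** The Protocol (Randomization, intervention, and masking) randomises equally to four arms: CsA, Tacrolimus, and each of these drops with LLLT.

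The SAP (Statistical analysis) states: "A one-way ANOVA with Bonferroni-adjusted post hoc tests was also performed to compare inter-group differences". It then defines the between-group quantity as the difference between the changes "observed within each group over the mentioned intervals was computed for each pair of groups", for baseline to month 6, baseline to month 12, and month 6 to month 12. On the threshold it says: "Statistical significance was defined as a P -value less than 0.05".

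The Bonferroni divisor is not printed. Six follows from taking every pair of four groups. No step-down procedure is named, and the SAP does not say whether the pairwise tests depend on a significant overall ANOVA.

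**The concern.** Single-step Bonferroni holds every pair to the threshold that only the smallest P-value needs to meet. Once one pair has been rejected, at most five true null hypotheses can remain, so dividing by six is stricter than 5% family-wise control requires. Holm uses this at no cost in assumptions.

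The contrasts at stake are LLLT-CsA v CsA and LLLT-Tacrolimus v Tacrolimus, which are the pairwise evidence for adding LLLT, and the two comparisons of one drop with the other. In arms of about 24, a moderate real difference in any of these can be missed under Bonferroni and found under Holm, from the same data and with the same error guarantee.

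**Working it through.** **Inputs.** From the SAP: threshold 0.05 (two-sided assumed); 24 per group ("a sample size of 24 eyes per group would yield a power" above 80%); planning difference "with a mean value of -8.05 ± 2.78 points (Range: -0.75 to -12.74"); "a statistically significant paired difference of 95% confidence". From the Protocol: four equal arms. Number of pairs: 4 × 3 / 2 = 6.

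**The plan's own figure.** If ± is an SD, d = 8.05/2.78 = 2.90. The usual two-group formula gives 2 × (1.960 + 0.842)² / 2.90² = 15.70/8.41 = 1.9, so 2 per group; the paired formula gives half that, so 1. The stated 24 is not reproduced, and the effect size it was built on cannot be recovered. The smaller effects below are therefore assumptions. The value d = 0.83 is what 24 per arm detects with 80% power at an unadjusted 5%. The value 0.92 is a somewhat larger alternative.

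**The two rules.** Bonferroni rejects every P at or below 0.05/6 = 0.0083. Holm orders the P-values and compares them in turn with 0.0083, 0.0100, 0.0125, 0.0167, 0.0250 and 0.0500, stopping at the first failure.

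- *Never fewer rejections.* A P-value at or below 0.0083 passes every later threshold, and so do all smaller ones. Holm keeps every Bonferroni rejection.
- *Same bound.* If k nulls are true, the first true null that Holm rejects was compared with at most 0.05/k. The Bonferroni inequality over those k nulls gives at most 0.05.
- *Same first step.* The chance of at least one rejection among the six is identical.

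**Check by hand for Bonferroni.** With 4 × 23 = 92 degrees of freedom the critical value is 2.697. The expected t is d × √(24/2) = 3.464d. At d = 0.826 this is 2.861, so power is about Φ(2.861 − 2.697) = Φ(0.164) = 57%. At d = 0.916 it is 3.173, giving Φ(0.476) = 68%.

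**Simulation.** Four arms of 24 independent units, equal SD, pooled-variance pairwise tests with no preliminary F-test, 60,000 to 100,000 trials per scenario. Repeat runs agree to about one point. Holm lost no Bonferroni rejection in any scenario.

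| Assumed truth | Quantity | Bonferroni, 6 pairs | Holm, same 6 |
|---|---|---|---|
| LLLT d = 0.83 with both drops, no drop difference | each LLLT contrast | 57% | 62% |
| | both LLLT contrasts | 33% | 42% |
| | at least one LLLT contrast | 81% | 82% |
| | any false drop difference | 1.6% | 2.8% |
| LLLT d = 0.92 with both drops, no drop difference | each / both LLLT contrasts | 68% / 47% | 74% / 57% |
| LLLT d = 0.83 with one drop only | the real LLLT contrast | 57% | 60% |
| LLLT d = 2.90, no drop difference | each LLLT contrast | >99.9% | >99.9% |
| | any false drop difference | 1.6% | 4.9% |
| LLLT d = 2.90, drop effect 0.8 | each / both drop contrasts | 53% / 29% | 75% / 61% |
| LLLT d = 2.90, drop effect 0.5 | each drop contrast | 18% | 33% |
| No differences at all | any false rejection | 4.0% | 4.0% |

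In the equal-effect scenario, the gain per LLLT contrast is about 2 points at d = 0.5 (17% to 19%) and 5 points at d = 1.0 (77% to 82%).

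The drop contrasts gain at d = 2.90 because four pairs are rejected almost surely, which leaves the last two to be tested at 0.0250 and 0.0500 instead of 0.0083.

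**The case against.** **The plan contains no error.** It names a correction and defines every contrast, and Bonferroni controls the family-wise error within each interval. This stands: the point is about efficiency.

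**At the SAP's planning effect the LLLT contrasts gain nothing.** This also stands. It does not extend to the drop contrasts, where the step-down gain is then largest.

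**Holm's extra rejections include false ones.** Attained family-wise error rises, for example from 1.6% to 4.9%. That is true, but it remains within the 5% the plan allows itself. Bonferroni also provides matching simultaneous intervals, and Holm has no simple counterpart.

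**The percentages rest on a favourable case.** An equal LLLT effect with both drops makes four of six pairs real, which helps a step-down rule; with one drop only, the gain is 3 points. The SAP also counts eyes, and its pilot had 20 eyes of 10 patients per group. If 24 eyes were 12 patients with fully correlated eyes, power at d = 0.83 would be about 24% against 27%. The direction is secure; the absolute figures are not.

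**Multiplicity elsewhere is untouched.** Three outcomes by three intervals make nine families. If independent, the chance of a false positive somewhere is up to 1 − 0.95⁹ = 37%. Holm within each family neither creates nor repairs this.

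**A reader might infer that the two mixed pairs should be dropped**, since LLLT-CsA v Tacrolimus and LLLT-Tacrolimus v CsA change drop and light together and isolate neither. The documents do not support requiring this. Those pairs compare whole regimens, a legitimate question in a four-arm active-controlled trial, and the SAP defines its contrasts for every pair. Cutting the family to four after the trial has ended would be a post hoc choice.

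**Conclusion.** The concern holds as a loss of efficiency in a valid analysis. Over the same six pairs, Holm gives the same 5% family-wise bound with at least as many rejections. That statement is exact and needs no effect-size assumption.

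The size of the gain does need assumptions. With 24 independent units per arm and an equal LLLT effect of d = 0.83 or 0.92 with both drops, it is about 5 to 6 points per LLLT contrast and about 9 to 10 points for both together. It is about 3 points if LLLT works with one drop only. At d = 2.90 it is nil for LLLT but 22 points per drop contrast (75% − 53%) at an assumed drop effect of 0.8.

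Two stronger readings should be resisted. One is that Bonferroni makes the results wrong: what it rejects, Holm also rejects. The other is that Holm always finds more: if the smallest P-value exceeds 0.0083, both rules reject nothing.

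**What to change.** In the SAP, Statistical analysis, change the adjustment of the between-group post hoc P-values from Bonferroni to Holm and keep all six pairs at each interval. Suitable wording: *For each outcome and interval, P-values for the six between-group pairs are adjusted by Holm's method.* Keep Bonferroni or Tukey for displayed simultaneous intervals. With 92 degrees of freedom the multipliers are 2.697 and 2.617, so Tukey intervals are about 3% narrower (2.617/2.697 = 0.970).

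The Protocol places the trial between May 2024 and June 2025, and the SAP is dated 10/13/2025 and written in the past tense. The change should therefore be disclosed as made after the trial, with Bonferroni-adjusted results beside the Holm results so that readers can see which conclusions depend on it.

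The cost is one SAP sentence, one extra column in the results table, and a sort-and-multiply step on the unadjusted pairwise P-values. No data or visits change. The drawbacks are that Holm P-values and the displayed intervals may occasionally disagree, and that attained error moves closer to 5%. Restricting the family to the four single-factor pairs is optional. If done now, it should be labelled post hoc.

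### Clinical relevance is judged only by Cohen's generic effect-size classes, which measure signal against spread and say nothing about how many OSDI points are gained

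*SAP*

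**What the plan says.** The last paragraph of the SAP's Statistical analysis section sets up two assessments, statistical significance (P below 0.05) and clinical relevance. On the second it says: "Clinical relevance was estimated using partial eta squared" for the ANOVAs, Cohen's "d_z for within-group comparisons", and Cohen's d_s for comparisons between groups. The grading follows: "According to Cohen's benchmarks, effect sizes were classified as small", moderate or large, with cut-offs of 0.06 and 0.14 for partial eta squared and of 0.50 and 0.80 for d. The d cut-offs are the same for d_z and d_s.

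The primary outcome (protocol, Assessment of the outcome measures) is the change in OSDI from baseline at months 6 and 12. Neither document gives an OSDI threshold for relevance, a responder definition, or a confidence interval for an effect size. The only OSDI difference stated is the planning value in the SAP's sample-size paragraph, "with a mean value of -8.05 ± 2.78 points". The SAP also defines the between-group difference in change (D_Δ) in original units for every pair of groups and every interval.

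**The concern.** A standardized effect is a difference divided by a standard deviation. It says how clearly groups separate relative to patient-to-patient variation, not how much a patient's symptoms improve. The same gain in OSDI points moves between classes as the sample becomes more or less homogeneous. For d_z it also moves with the correlation between visits. Because the classes are applied to point estimates, a class can be assigned to a value that is mostly noise.

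What is at stake is one of the two conclusions the SAP sets out to draw. The P-values are not affected. A statement that a treatment difference is, or is not, clinically relevant would have no basis in OSDI points.

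**Working it through.** **Inputs.** From the SAP: planned difference 8.05 with ± 2.78 (not identified as SD or SE, nor of which quantity); 24 eyes per group; power above 80%; 95% confidence; Cohen cut-offs 0.50/0.80 and 0.06/0.14. From the protocol: four groups, hence six pairs. Assumed: two-sided alpha 0.05 and a two-sample comparison.

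**1. Does 2.78 act as the SD of change in the plan's own sample size?** Normal formula: n = 2 × (1.96 + 0.84)² × (2.78/8.05)² = 1.9, so 2 per group. The exact t calculation gives 4 per group (92% power). Neither is near 24, so 2.78 cannot be taken as the SD behind the sample size. Working backwards, 24 per group has 80% power at d = 0.826 (exact t), so SD = 8.05/0.826 = 9.7. The normal approximation gives 9.95. The failure to reproduce 24 is a separate matter; here it only shows that the SD is unknown.

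**2. OSDI points at the cut-offs for d_s** (cut-off × SD of change):

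| SD of change | *Moderate* from | *Large* from | *Large* as share of 8.05 |
|---|---|---|---|
| 2.78 (if it is that SD) | 1.39 | 2.22 | 28% |
| 5 (illustrative) | 2.50 | 4.00 | 50% |
| 9.74 (back-solved) | 4.87 | 7.79 | 97% |

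**3. Precision.** An observed d_s of exactly 0.80 with 24 per arm has a 95% CI of 0.21 to 1.38 (noncentral t). At SD 2.78 the mean difference is 2.22 points, with a 95% CI of about 0.6 to 3.8.

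**4. Same cut-offs for d_z and d_s.** With equal SDs at both visits and correlation r, the SD of change is SD × √(2(1 − r)). A *large* d_z therefore needs a change of 0.8 × √(2(1 − r)) visit SDs:
- r = 0.3: 0.8 × √1.4 = 0.95 SD
- r = 0.9: 0.8 × √0.2 = 0.36 SD

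**5. Labels by chance, no true effect, 24 independent values per arm.** For one pair, t = d_s × √(24/2) on 46 df:
- d_s at least 0.5: t = 1.73, probability 9.0%; any of six pairs at one interval, about 32% (simulation, 20,000 runs)
- d_s at least 0.8: t = 2.77, probability 0.8%; any of six pairs, about 4%

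For the one-way ANOVA, F = (η/3)/((1 − η)/92), where η is partial eta squared:
- η at least 0.06: F = 1.96, probability 12.6%
- η at least 0.14: F = 4.99, probability 0.3%

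**6. If the 24 eyes are 12 patients with one OSDI score each (an assumption).** t = d_s × √(12/2) on 22 df. At least 0.5: t = 1.22, 23% per pair. At least 0.8: t = 1.96, 6.3% per pair, and about 26% for any of six pairs (simulation).

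**The case against.** A reader might infer three stronger things that the documents do not support.

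- *That a large label is easily reached by chance.* With 24 independent values per arm it is not. The smallest d_s that is significant after Bonferroni adjustment for six pairs is about 0.78 to 0.80, so *large* is about as strict as the adjusted test. The exception is the eyes-as-patients assumption in step 6, which is a unit-of-analysis problem of its own.
- *That a large label starts at about a quarter of the planned difference.* This needs 2.78 to be the between-patient SD of change. The SAP does not say so, and step 1 makes it doubtful. At the back-solved SD, *large* starts near the full planned difference.
- *That the plan will declare large effects clinically relevant.* The SAP classifies effect sizes and does not say which class counts as relevant. The link is a fair inference, because no other rule is given, but it is an inference.

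It can also be said that P-values are assessed alongside, that D_Δ is already planned in original units, and that the SAP does not propose comparing d_z labels with d_s labels. All three are true and they limit the damage. They do not repair the rule. Relevance is a separate assessment that is not made conditional on P below 0.05. D_Δ has no threshold or CI attached. The dependence of d_z on r affects each within-group label even if it is never set beside a d_s label.

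**Conclusion.** The point holds as a defect in the relevance criterion. Taken as written, the SAP has no basis for a conclusion on clinical relevance, because its only criterion depends on the observed spread and, within groups, on the visit-to-visit correlation. In points, *large* could begin anywhere from 2.2 (if 2.78 is the SD of change) to 7.8 (if that SD is 9.7), and the documents do not settle which. The d_z result is algebra and needs only equal SDs at the two visits. The chance problem applies to *moderate*; for *large* it arises only under the assumption of 12 patients per arm. The defect is worth correcting because the remedy is cheap. It does not affect the significance tests.

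**What to change.** Rewrite the effect-size paragraph of the SAP as follows.

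1. Stop calling partial eta squared, d_z and d_s measures of clinical relevance. Keep them as descriptive figures, and do not apply the d_s cut-offs to d_z.
2. Report D_ΔM6 and D_ΔM12 between groups in OSDI points with 95% CIs.
3. Judge relevance against one threshold in OSDI points that the sponsor justifies from outside this trial's data. Do not use 8.05 by default. It is a pilot-based planning difference, and if the whole CI had to lie beyond it, a true effect of exactly 8.05 would qualify only about 2.5% of the time.
4. State the decision rule before applying it. For example: relevance shown if the whole CI lies beyond the threshold in the direction of benefit, not shown if the whole CI falls short of it, and inconclusive otherwise.
5. Disclose that the threshold was set after data collection. The protocol gives the trial period as May 2024 to June 2025, and both documents are dated 10/13/2025.

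The cost is one rewritten paragraph and confidence intervals for differences already being computed. The downside is small: fewer effects will be called clinically relevant, and the threshold is post hoc however well it is justified.
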